5.3.6 Convergence Considerations for RBMI-Based Analyses

In the rare situation that the imputation model (see step 1, imputation model, in Section 5.3.3) would fail to converge despite the attempt to simplify the variance-covariance

matrix, it will be investigated whether removing some covariates and/or pooling factor levels of categorical covariates would solve the issue.

In case the root cause of the problem could not be attributed to the choice of covariates, the following approaches will be tried in sequence:

- *Replace jackknife with bootstrap, and accept up to a maximum of 5% failed runs (out of the total number of bootstrap runs). Runs that did fail would be discarded.*
- *Derive only a point estimate based on the conditional mean imputation, but no standard error (as jackknife and bootstrap did not work)*

5.4 SECONDARY ENDPOINTS ANALYSES

The same primary estimand's analysis strategy (see Section 5.3.2) will be applied to secondary endpoints listed in Table 5, with the following exceptions for the corresponding estimator:

- *the imputation model will not include, as covariates, the baseline ADAS-Cog 13 total score and the baseline ADCS-ADL total score*

The imputation model will thus include treatment group, visit, and treatment-by-visit interaction, the baseline score and the baseline score-by-visit interaction, and the randomization stratification factors, namely: disease stage, geographic region, the use of AD medication at baseline and the APOE ε4 status

- *the analysis model will not include, as covariates, the baseline ADAS-Cog 13 total score and the baseline ADCS-ADL total score*

The analysis model will thus include treatment, the baseline score and the randomization stratification factors, namely: disease stage, geographic region, the use of AD medication at baseline and the APOE ε4 status

In the following, confirmatory secondary endpoints refer to endpoints included in the type I error control procedure. Other important secondary endpoints not subject to the type I error control procedure are considered as supportive secondary endpoints. For all secondary endpoints, the treatment effect over time will also be considered and the change from baseline to Weeks 24, 52, 76, and 104 will be provided as supplementary analyses.

Table 5 Secondary Endpoints

| Secondary Efficacy Endpoint | Confirmatory | Type |
|---|---------------------|-------------|
| Alzheimer's Disease Assessment Scale, Cognitive subscale, 13-item (ADAS-Cog 13) | yes | Continuous |
| Alzheimer's Disease Cooperative Study, Activities of Daily Living scale (ADCS-ADL) total score | yes | Continuous |
| Functional Activities Questionnaire (FAQ) | yes | Continuous |
| Mini Mental State Examination (MMSE) | no | Continuous |
| Alzheimer's Disease Assessment Scale, Cognitive subscale, 11-item (ADAS-Cog 11) | no | Continuous |
| Coding (Digit Symbol Substitution Test [DSST]) | no | Continuous |
| Verbal Fluency Task | no | Continuous |
| Alzheimer's Disease Cooperative Study, Activities of Daily Living scale (ADCS-ADL) instrumental score | no | Continuous |

ADAS-Cog 13= Alzheimer's Disease Assessment Scale, Cognitive subscale, 13-item; ADCS-ADL= Alzheimer's Disease Cooperative Study, Activities of Daily Living scale; ADAS-Cog 11= Alzheimer's Disease Assessment Scale, Cognitive subscale; DSST= Digit Symbol Substitution Test; FAQ= Functional Activities Questionnaire; MMSE= Mini Mental State Examination.

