3. SAMPLE SIZE DETERMINATION

Determination of sample size is based on participants enrolled in the global enrollment phase. In each study, approximately 1016 participants will be enrolled and randomized in 1:1 ratio to each treatment arm (active drug or placebo) during the global enrollment phase. The original planned sample size was of 760 participants, but it was increased to 1016 participants based on considerations from external studies (in protocol version 3).

Additional participants may be randomized during the China extension if at least 1 participant is enrolled at sites in mainland China, Hong Kong, or Taiwan that are recognized by the NMPA during the global enrollment phase.

The estimated sample size required to demonstrate efficacy with regard to Clinical Dementia Rating-Sum of Boxes (CDR-SB) is based on the following assumptions:

- the mean change in the CDR-SB from baseline to Week 104 is 2.5 points in the placebo arm
- a common standard deviation across treatment arms for change of approximately 2.97 from baseline to Week 104 in the CDR-SB
- active drug has a true effect of a 30% relative reduction in deterioration of CDR-SB

Based on these assumptions, and using a student's T-test with equal variance, a sample size was calculated for 90% power to detect a true treatment effect of 30% relative reduction in deterioration of CDR-SB at a two-sided α of 0.05.

Uncertainties on parameters affecting the power (e.g., dropout rate, study drug discontinuation rate, standard deviation, and placebo decline) were assumed to be equivalent to a drop in sample size of up to around 35% and were corrected for accordingly. This calculation leads to a total of 1016 participants in the study.

At the date of writing Protocol Version 4, it was expected that participants would miss an average of 8 weeks of study drug administration over the course of the original two-year study due to the COVID-19 pandemic. This had the potential to decrease the power of the study from ~90% to ~80%. To mitigate the impact of missed administrations, the double-blind treatment period has been extended by 12 weeks. Under current assumptions, this brings the study power back to the originally planned ~90%.

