The imputation model includes the following covariates: treatment group, visit, and treatment-by-visit interaction, baseline CDR-SB score and baseline CDR-SB score-by-visit interaction, baseline ADAS-Cog 13 total score, baseline ADCS-ADL total score and the randomization stratification factors, namely: disease stage (from the eCRF), geographic region (from the IxRS), the use of AD medication at baseline (derived from the eCRF based on a search of medications; see below for more details) and the APOE ε4 status (from the Vendor). For geographic region, IxRS is preferred over the eCRF source, to keep the “starting” region for analysis, in case a participant moved to a different region during the study (the eCRF would otherwise reflect the “final” region). AD medication at baseline will be defined as any use of donepezil, galantamine, memantine or rivastigmine prior to randomization and with an

end date not before the randomization date. An unstructured variance-covariance structure will be applied to model the within-subject errors across visits. If the model fails to converge, then a heterogeneous Toeplitz covariance structure will be used instead and if this still fails, then a compound symmetry covariance structure will be used.

Imputations will be based on restricted maximum likelihood (REML) estimation of the regression and covariance parameters from the imputation model ([von Hippel and Bartlett 2021](#); [Wang and Robins 1998](#)).

2. Imputation step

The imputation model implies a marginal multivariate normal distribution of the longitudinal outcome values across all visits based on a participant's assigned treatment arm and covariate values. This marginal imputation distribution will be used for all participants in the placebo arm and all participants in the active drug arm without an SDCR ICE. For participants in the active drug arm with an SDCR ICE, the mean of the marginal imputation distribution for outcomes after the SDCR ICE will be modified as per the CIR assumption ([Carpenter et al. 2013](#)).

For each participant, the conditional imputation distribution of their missing outcome values is defined as the marginal imputation distribution conditional on the participant's observed outcomes (including observed post-SDCR ICE outcome assessments). A single deterministic imputation using the conditional mean from the conditional imputation distribution for each participant with missing outcomes will be used.

3. Analysis step

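### The confirmatory secondary models leave out, without a stated reason, baseline scales that the primary model adjusts for, and may lose a little precision by it

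*SAP*

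**What the plan says.** For the primary endpoint, SAP Section 5.3.3 fits an MMRM imputation model and then an ANCOVA on the completed Week 116 data. Besides treatment, both adjust for baseline CDR-SB, "baseline ADAS-Cog 13 total score, baseline ADCS-ADL total score and the randomization stratification factors" (disease stage, region, AD medication and APOE ε4 status).

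Section 5.4 carries this strategy over to the secondary endpoints with two exceptions. First, "the imputation model will not include, as covariates, the baseline ADAS-Cog 13 total score and the baseline ADCS-ADL total score". Second, "the analysis model will not include, as covariates, the baseline ADAS-Cog 13 total score and the baseline ADCS-ADL total score". After each exception it lists what remains: treatment, the endpoint's own baseline and the stratification factors, plus the visit terms in the imputation model. The exceptions have to be read with those lists. Taken alone, they would bar baseline ADAS-Cog 13 from the ADAS-Cog 13 model, which the list plainly retains.

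Three secondaries are confirmatory. Under Section 5.1 they are tested in fixed sequence after CDR-SB: ADAS-Cog 13, then ADCS-ADL total, then FAQ. The supplementary MMRM for them in Section 5.4.1 uses the same reduced set. Neither Section 5.4 nor the SAP amendment table gives a reason for the reduction; the table says only that estimator detail was added for clarity.

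**The concern.** Adjusting for prognostic baseline variables is a standard way to gain precision in a randomised comparison, and the primary model does so with a cognitive and a functional scale. Baseline function plausibly predicts later cognitive decline, and baseline cognition later functional decline. Leaving these scales out of the secondary models would then give wider confidence intervals than necessary.

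Two features raise the stakes slightly. The three secondaries are the only others under alpha control, so a miss on ADAS-Cog 13 stops the testing of ADCS-ADL and FAQ. Imputation also carries some weight: the simulation scenarios in SAP Appendix 1 use overall intercurrent-event probabilities of 26% to 36% per arm, with 80% drop-out after study-drug- or condition-related events. Extra prognostic baselines could make those imputations better informed.

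**Working it through.** **1. The plan's own figure.** SAP Section 3 states a sample size for CDR-SB only. Inputs:
- "the mean change in the CDR-SB from baseline to Week 104 is 2.5 points in the placebo arm"
- "active drug has a true effect of a 30% relative reduction in deterioration of CDR-SB", so the difference is 0.30 × 2.5 = 0.75
- "a common standard deviation across treatment arms for change of approximately 2.97"
- "a sample size was calculated for 90% power" "at a two-sided α of 0.05"
- an allowance of about 35% for dropout and other uncertainty

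n per arm = 2 × (1.960 + 1.282)² × 2.97² / 0.75² = 329.6, rounded up to 330. Then 330 / 0.65 = 507.7, rounded up to 508 per arm, or 1016 in total. This matches the plan. (An exact noncentral-t calculation gives 331 per arm and 1020 after inflation.) The calculation is an unadjusted t-test on CDR-SB, so it neither depends on nor tests the secondary covariate sets. No SD, effect or power is stated for any secondary.

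**2. What each confirmatory model loses.**

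| Endpoint | Baseline scale kept | Primary-model scale absent |
|---|---|---|
| ADAS-Cog 13 | ADAS-Cog 13 | ADCS-ADL |
| ADCS-ADL total | ADCS-ADL | ADAS-Cog 13 |
| FAQ | FAQ | ADAS-Cog 13 and ADCS-ADL |

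All three keep disease stage and the other stratification factors.

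**3. Size of the loss.** Let r be the partial correlation (for FAQ, the multiple partial correlation) of the absent scale or scales with the Week 116 outcome, given the covariates already in the model. The documents do not give r, so the range is an assumption. The 80% and 90% starting powers are illustrative. The formulas are the complete-data ANCOVA approximation:
- SE ratio = √(1 − r²)
- equivalent gain in N = 1/(1 − r²) − 1
- power = Φ[(1.960 + z) / √(1 − r²) − 1.960], with z = 0.842 for 80% and 1.282 for 90%

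| r (assumed) | SE reduction | Equivalent N | Power from 80% | Power from 90% |
|---|---|---|---|---|
| 0 | 0% | 0% | 80.0% | 90.0% |
| 0.1 | 0.5% | +1.0% | 80.4% | 90.3% |
| 0.2 | 2.0% | +4.2% | 81.6% | 91.1% |
| 0.3 | 4.6% | +9.9% | 83.6% | 92.5% |

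For r = 0.3 from 80%: 2.802 / 0.954 − 1.960 = 0.977, and Φ(0.977) = 0.836.

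**4. Is 0 to 0.3 a sensible range?** SAP Appendix 1 simulates a correlation of 0.52 between the baseline and Week 116 values of the outcome. Borrow that figure, and let a second scale correlate c with the own baseline and b with Week 116 (both assumed). Then r = (b − 0.52c) / √[(1 − 0.52²)(1 − c²)].
- c = 0.6, b = 0.30: r = −0.02
- c = 0.5, b = 0.40: r = 0.19
- c = 0.4, b = 0.45: r = 0.31

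So r runs from about zero to about 0.3. This does not account for disease stage, which also carries severity and would probably lower r.

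**5. Cost of including the scales.** CDR, ADAS-Cog 13 and ADCS-ADL are scheduled at baseline (Protocol Section 4.6.2 and Appendix 1, Table 1). Under SAP Section 5.1, a missing baseline covariate other than the endpoint's own baseline is set to the overall median, so no participant is lost. As main effects, the two scales add one term for ADAS-Cog 13, one for ADCS-ADL and two for FAQ. Optional baseline CDR-SB makes these two, two and three.

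**The case against.** The strongest reply is that this is a choice and not an error. The reduced set is pre-specified, stated for both models, and used consistently in the supplementary MMRM and for the exploratory endpoints. A smaller uniform model across eight endpoints, each refitted under the jackknife with an unstructured covariance, is a plausible motive. The imputation also conditions on each participant's own observed outcomes, which already carry severity and trajectory, so the added information may be small. The secondaries are reached only if CDR-SB succeeds.

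Much of this stands, and it limits the point to efficiency. The convergence and uniformity motive is not in the SAP, however. Section 5.3.6 treats failure of the imputation model as rare and already allows covariates to be removed if it happens, so removing them in advance is not needed for that purpose. Some supportive endpoints do nearly duplicate the excluded scales (ADAS-Cog 11, the ADCS-ADL instrumental score), but that does not apply to the three confirmatory ones.

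A reader might infer more than the documents support:
- That every secondary model discards both cognition and function. Only FAQ loses both named scales, and it keeps its own functional baseline.
- That baseline CDR-SB was taken away. In the primary model it is the endpoint's own baseline, and each secondary's own baseline takes that place. Adding CDR-SB would be an extra, not a restoration.
- That the reduction has no benefit at all. The plan is silent on its reason, and silence does not show that none exists.
- That the precision loss is established. It rests on correlations the documents do not give.

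**Conclusion.** The point holds as an optional improvement. The plan omits, without explanation, baseline scales that it treats as worth adjusting for in the primary analysis, and including them would be almost free. The omission does not bias the randomised comparison, inflate type I error, change the 1016 or affect the CDR-SB analysis.

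The gain cannot be fixed from the documents. It could be close to zero. Over the assumed range it reaches 4.6% in standard error, or about 3.6 power points from an assumed 80%. Any further benefit through better-informed imputation is plausible but not quantified here.

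**What to change.** Before unblinding, amend SAP Section 5.4 for ADAS-Cog 13, ADCS-ADL total and FAQ. Include baseline ADAS-Cog 13 and baseline ADCS-ADL in both the imputation model and the ANCOVA, alongside the endpoint's own baseline and the stratification factors. Baseline CDR-SB may be added as a further prognostic covariate. Make the same change to the supplementary MMRM in Section 5.4.1, and rely on the existing rule in Section 5.3.6 if an imputation model fails to converge. The supportive endpoints can stay as they are. If the sponsor prefers the reduced set, state the reason.

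The cost is a few lines of SAP text, matching program changes, and at most two or three degrees of freedom out of about 1,016 participants. No new data are needed.

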5.4.1 Confirmatory Secondary Endpoints

The confirmatory secondary endpoints are provided to increase the confidence in the treatment effect observed on the primary endpoint. For these confirmatory secondary endpoints, *as already outlined in the beginning of Section 5.4, the same primary estimand's strategy will be applied, with some changes to the corresponding estimator (see Section 5.4 for the details).*

For these confirmatory secondary endpoints, MMRM analyses will also be considered as supplementary analyses. In this case, the change from baseline in the confirmatory secondary endpoints will be adjusted on the following covariates: treatment group, visit, treatment-by-visit interaction, the respective baseline score for each secondary endpoint, the baseline score-by-visit interaction and the randomization stratification factors as specified for the primary endpoint, see Section 5.3.4, paragraph on MMRM.

The method for controlling the overall Type I error is described in section 5.1.

5.4.1.1 Alzheimer's Disease Assessment Scale, Cognitive Subscale, 11- item and 13-Item (ADAS-Cog 11/ ADAS-Cog 13)

The ADAS-Cog is the most frequently used scale to assess cognition in clinical trials for mild to moderate AD dementia ([Rozzini et al. 2007](#); [Connor and Sabbagh 2008](#); [Ihl et al.](#)

2012). More specifically, the ADAS-Cog is a participant-based assessment that measures learning and memory, language production, language comprehension, constructional praxis, ideational praxis, and orientation. The modified version will be used; it has 13 items and includes the addition of delayed word recall and a number of cancellation subtests, as well as use of only one trial for word recognition (Mohs et al. 1997). Equivalent alternate forms of the word recall, word recognition, and number cancellation subtests will be used in successive test administrations. The ADAS-Cog 11 and 13 will be used in this study, with ADAS-Cog 13 considered as a confirmatory secondary endpoint. Individual item scores are based on errors and generally range from 1 to 5, although some items have smaller or larger score ranges. The ADAS-Cog 13 total score ranges from 0-85, with higher scores reflecting greater impairment. It takes approximately 45 min to administer the ADAS-Cog 13.

5.4.1.2 Alzheimer’s Disease Cooperative Study, Activities of Daily Living Scale (ADCS-ADL), Total Score

The ADCS-ADL (Galasko et al. 1997) is the scale most widely used to assess functional outcome in participants with AD (Vellas et al. 2008). The ADCS-ADL is a 23-item informant-based questionnaire that covers both basic activities of daily living (ADL) (e.g., eating and toileting) and more complex ADL or instrumental ADL (e.g., using the telephone, managing finances, preparing a meal). It has a 4-week recall period. Total scores range from 0-78, with higher scores indicating better functioning.

5.4.1.3 Functional Activities Questionnaire (FAQ)

The FAQ (Pfeffer et al. 1982) is an informant-based measure of functional abilities. Informants provide performance ratings of the target person on ten complex higher-order activities. The FAQ is a 30-point scale, the higher the score the worse the performance.

5.4.2 Supportive Secondary Endpoints

For context, additional clinical endpoints collected longitudinally in the studies will be provided (see Table 5). The Sponsor proposes not to rank these hierarchically as for confirmatory secondary endpoints.

5.4.2.1 Mini Mental State Examination (MMSE)

The MMSE is a set of standardized questions used to evaluate possible cognitive impairment and help stage the severity level of this impairment (Folstein et al. 1975). The questions target six areas: orientation, registration, attention, short-term recall, language, and constructional praxis/visuospatial abilities. The MMSE is a participant-based assessment. The score ranges from 0-30, with lower values indicating a greater impairment.

5.4.2.2 Digit Symbol Substitution Test (DSST)

Coding, also called Digit Symbol Substitution Test (or DSST), is a subtest from the Wechsler Adult Intelligence Scale-Fourth Edition (WAIS-IV; Wechsler 2008). Coding is a participant-based assessment that measures speed of processing and associative

memory. The test is known to be sensitive to disease progression (Lezak et al. 2004). The 120-second version of the test will be used in this study.

5.4.2.3 Verbal Fluency Task

The category verbal fluency (e.g., animals) is a participant-based assessment that measures speed and flexibility of verbal thought. Verbal fluency tests are sensitive tools for detecting dementia (Pasquier et al. 1995; Lezak et al. 2004) and for monitoring decline over time (Clark et al. 2009).

5.4.2.4 Alzheimer’s Disease Cooperative Study, Activities of Daily Living Scale (ADCS-ADL), Instrumental Score

The ADCS-ADL instrumental score is a sub score of the ADCS-ADL scale, see Section 5.4.1.2. The ADCS-ADL instrumental score used in this study is the sum of items 6a and 7 to 23.

5.4.3 COVID-19 Related Sensitivity Analyses for Secondary Endpoints

During the COVID-19 pandemic, many countries took movements’ restriction policy. Among the clinical outcomes collected in the study, some questionnaires may be particularly impacted. These questionnaires include items describing actions that are strongly constrained or prohibited by restriction policies.

We define modified versions of the total score for these scales. These modified scales scores may be used to perform sensitivity analysis aiming at understanding and mitigating the impact of the COVID-19 pandemic on study results and interpretation, in line with the primary clinical question of interest.

5.4.3.1 ADCS-ADL COVID-19 Modified Total Score

The original ADCS-ADL is a 23 item scale with a total score range of 0-78. The following items were identified as being particularly impacted by the pandemic related restrictions:

- Item 2: Optimal walking performance, maximum 3 points
- Item 15: Optimal performance getting around/travelling outside the home, maximum 4 points
- Item 16a/b: Shopping trips - selecting items and paying without supervision, maximum 4 points
- Item 18: Left away from home, maximum 3 point

A sensitivity analysis may be conducted, using a modified version of the ADCS-ADL total score after removing of these four items, resulting in a 19-item scale with a score range of 0-64. This alternative version will be referred to as “ADCS-ADL COVID-19 modified total score”.

5.4.3.2 FAQ COVID-19 Modified Total Score

The original FAQ is a 10-item scale with a score range of 0-30. The following items were identified as being particularly impacted by the pandemic related restrictions:

- Item 3: Shopping alone, maximum 3 points
- Item 10: Travelling outside of the neighborhood, maximum 3 points

A sensitivity analysis may be conducted, using a modified version of the FAQ total score after removing of these 2 items, resulting in an 8-item scale with a score range of 0-24. This alternative version will be referred to as “FAQ COVID-19 modified total score”.

5.5 EXPLORATORY ENDPOINT(S) ANALYSIS

The same primary estimand’s analysis strategy (see Section 5.3.2) will be applied to continuous exploratory endpoints listed in Table 6, with the following exceptions for the corresponding estimator:

- . the imputation model will not include, as covariates, the baseline ADAS-Cog 13 total score and the baseline ADCS-ADL total score

The imputation model will thus include treatment group, visit, and treatment-by-visit interaction, the baseline score and the baseline score-by-visit interaction, and the randomization stratification factors, namely: disease stage, geographic region, the use of AD medication at baseline and the APOE ε4 status

- the analysis model will not include, as covariates, the baseline ADAS-Cog 13 total score and the baseline ADCS-ADL total score

The analysis model will thus include treatment, the baseline score and the randomization stratification factors, namely: disease stage, geographic region, the use of AD medication at baseline and the APOE ε4 status

. For all continuous exploratory endpoints, the ANCOVA analysis model will include the baseline score of the exploratory endpoint, the disease stage, geographic region, the use of AD medication at baseline and the APOE ε4 status as covariates.

For ordinal endpoints, only descriptive analyses will be considered, summarizing the frequencies of the different categories, as well the proportion of participants with a certain shift in categories.

The Resource Utilization in Dementia Scale–Lite (RUD-Lite) and the EuroQoL–5 Dimensions (EQ-5D-5L) scales will be used in this study for informing pharmacoeconomic evaluations and will be reported separately.

Table 6 Exploratory Endpoints

| Exploratory Efficacy Endpoint | Type |
|--|-------------|
| Clinical Dementia Rating-Global Score (CDR-GS) | Ordinal |
| CDR-Individual Components | Continuous |
| Dependency Level, as assessed by the Alzheimer disease cooperative study - activities of daily living (ADCS-ADL) score | Ordinal |
| Integrated AD Rating Scale (iADRS) | Continuous |
| Quality of Life–Alzheimer’s Disease (QoL-AD) | Continuous |
| Neuropsychiatric Inventory Questionnaire (NPI-Q) | Continuous |
| Zarit Caregiver Interview–Alzheimer’s Disease (ZCI-AD) | Continuous |

ADCS-ADL = Alzheimer disease cooperative study-activities of daily living; ADCOMS = AD Composite Score; CDR-GS =Clinical Dementia Rating-Global Score; EQ-5D= EuroQoL–5 Dimensions; iADRS = Integrated AD Rating Scale; NPI-Q= Neuropsychiatric Inventory Questionnaire ; QoL-AD =Quality of Life–Alzheimer’s Disease; ZCI-AD=Zarit Caregiver Interview–Alzheimer’s Disease.

